1.3 Schedule of Activities

Timeline for the Thrive study

Schedule of Assessments for the Thrive Study

	Screen	Consent	Baseline (T1)	Tech 1 (T2)	Tech 2 (T3)	Tech 3 (T4)	Tech 4 (T5)	Post-study (T6)	1 Mo (T7)	3 Mo (T8)
Eligibility	X									
Randomization		X								
Informed Consent		X								
Demographics		X								
Outcome Evaluations*										
Technology sessions - Positive Engagement (self-report)				X	X	X	X			
Technology sessions - Positive engagement (behavioral coding)				X	X	X	X			
Quality of Life			X	X	X	X	X	X	X	X
Mental Health			X	X	X	X	X	X	X	X
Thriving			X					X	X	X
Loneliness and social connection			X	X	X	X	X	X	X	X
Caregiver Guilt			X	X	X	X	X	X	X	X
Family bonding			X	X	X	X	X	X	X	X

* The outcomes listed above refer to general constructs rather than specific measures. Most outcomes will be measured using more than one self-report and/or behavioral assessment.

2 Introduction

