was in the LifeStory VR session. However, residents with dementia reported being more immersed in the VR sessions than residents with MCI. It could be that as the dementia becomes increasingly severe, it is more likely to restrict residents' bodily movements. However, dementia might enable residents to become more immersed in another world than if they have MCI. These speculations need to be tested with a larger sample in Phase II. We also did not have a large enough sample to test for differences between the two groups for quality of life indices. Therefore, research questions are posed instead of hypotheses. Phase II extends the literature by examining whether the impact of VR on residents' quality of life depends on their level of cognitive impairment, primarily because of the level of engagement. Likewise, the adult child's quality of life might also improve because of jointly benefiting from engagement in the VR with one's parent. Finally, Rendever should produce greater engagement than video chat because of the shared immersion into an altered reality. Therefore, our second aim and research questions are:

AIM2: *Determine whether the positive effects of Rendever (vs. control) on residents' and their adult children's quality of life depends upon residents' level of cognitive impairment (MCI vs. mild to moderate AD/ADRD).*

- **RQ1:** Are the effects of the VR condition (vs. control) on **quality of life moderated** by residents' level of cognitive impairment (MCI vs. mild to moderate AD/ADRD) both concurrently and over time (relative to baseline)?
- **RQ2:** If the effects of the VR condition (vs. control) on **quality of life** are moderated by residents' level of cognitive impairment, are these differences **mediated** by (explained by) group differences in **positive engagement**?

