Finally, having parents move into a senior living community can be stressful and anxiety-producing for adult children. We focus on residents of senior living communities and their adult children living at a distance because the distance can make it challenging to maintain their relationship and difficult for the adult children to feel like they have control over the quality of care provided for their parents. Adult children who cannot easily visit their parents and monitor their care often experience care-giver guilt. They feel guilty and anxious that their parent is in a senior living community and report dissatisfaction with information they receive about their parent's care.²⁴ Adult children's guilt, worry, and stress about their parent's safety and care has been exacerbated with COVID-19 because the disease can spread rapidly in these communities and put its entire population at risk. Adult children have also been unable to physically visit their parents because of the pandemic, further contributing to their existing anxiety and guilt. To improve the quality of life of the resident and ease the concerns of the adult child, it is essential that the senior living community involve the adult child in the parent's care and provide programming that allows residents to experience a high quality of life. The synergy that is created through the shared VR experiences should reduce caregiver guilt for the adult child not only because the child is engaged in the VR with their parent, but also because they see first-hand the positive effects that it has on their parent's engagement over time. Thus, our final aim and hypotheses are posed:

AIM3: *Determine whether Rendever (vs. control) reduces caregiver guilt for adult children who live at a distance, and whether these effects depend on the adult child's own response to the VR and their parent's response to the VR (a dyadic effect).*

- **H2a:** Adult children in the VR condition (vs. control) will show significantly **greater reductions in caregiver guilt** both concurrently and over time (relative to baseline).

H2b: The effects of the VR condition (vs. control) on **adult children' caregiver guilt** will be **moderated** by the adult child's own **positive engagement** and the parent's positive engagement, such that the beneficial effects of the VR condition will be amplified when positive engagement is higher (vs. lower) for self and parent (a dyadic effect)

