Determine whether the different forms of technology (VR vs. VC) have different immediate impacts on positive engagement and family bonding during the technology sessions, and whether these immediate responses mediate any impacts of the intervention on parent and adult child outcomes.	
• Self-reported emotional and social engagement during the intervention sessions• Observational and computer coding of social and behavioral (kinesic) engagement during the interventions sessions	Each measure is an outcome variable to test the secondary objectives.

4 Study Design

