4.1 Overall Design

Purpose of the clinical trial: The virtual reality (VR) program, Rendever, enables older adults in senior living communities to maintain important family relationships, engage fully with life, and reconnect with their past, regardless of physical location, through its advanced networking and live streaming capabilities. This Phase II project will continue to refine the long-distance features of Rendever, while expanding the scientific goals of the project by testing the immediate and longer-term impact of Rendever on the quality of life of residents and their adult children in an experimental design. The study will also continue to investigate whether residents' responses to the VR depend upon their level of cognitive impairment.

Study Design: The design of this study is a 2 (Intervention Group: Virtual Reality vs. Active Control) x 2 (Level of Cognitive Impairment: MCI vs. AD/ADR) x Time (7 time points) design. Participants will be older adults (age 50+) with mild cognitive impairments (MCI) or mild to moderate Alzheimer's Disease or related dementias (AD/ADR) who reside in senior living communities, and an adult child who lives at a distance. Residents will participate from a private room located in their senior living community. Adult children (age 18+) will participate from their own home, at least 45 minutes driving distance away. Resident-adult child dyads will be randomly assigned to an intervention group (Virtual Reality vs. Control) using a random number generator. Dependent variables will include measures of quality of life (quality of life, thriving, depression, mental health, positive and negative affectivity, loneliness, and social connection), family bonding (closeness, satisfaction, communal coping), and caregiver guilt (guilt, stress, and burden) assessed through surveys and interviews over the 4-month study period. Secondary outcome measures will include positive engagement *during the technology sessions* (positive affect, engagement with the technology and with the adult child while using it, emotional closeness) measured through surveys, interviews, and observational methods during the intervention phase of the study.

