6.3 Measures to Minimize Bias: Randomization and Blinding

Stratified Block Randomization Schedule (created with R “randomizeR” package):

- Strata = 4 (UCSB/Rendever x MCI/Dementia)
- Groups (VR/Zoom) = 2 | Block size = 4 (resulting in 6 possible combinations to draw from)
- Iterations (sequences) = 12 | 12 sequences of 4 = 48 subjects
- Results = 48 subjects per strata (equal allocation to conditions)
- Total N = 48 subjects x 4 strata = **192 dyads**

“A” = VR “B” = Zoom

UCSB – MCI	UCSB – DEMENTIA
[1] "A" "B" "B" "A"	[1] "B" "A" "B" "A"
[2] "A" "B" "A" "B"	[2] "B" "A" "A" "B"
[3] "B" "A" "A" "B"	[3] "B" "A" "B" "A"
[4] "B" "A" "A" "B"	[4] "B" "A" "B" "A"
[5] "B" "A" "A" "B"	[5] "B" "B" "A" "A"
[6] "B" "A" "B" "A"	[6] "B" "A" "B" "A"
[7] "B" "A" "B" "A"	[7] "B" "A" "A" "B"
[8] "A" "B" "A" "B"	[8] "A" "A" "B" "B"
[9] "B" "B" "A" "A"	[9] "B" "A" "B" "A"
[10] "B" "A" "A" "B"	[10] "B" "A" "B" "A"
[11] "A" "A" "B" "B"	[11] "A" "B" "A" "B"
[12] "B" "B" "A" "A"	[12] "A" "A" "B" "B"

RENDEVER – MCI	RENDEVER – DEMENTIA
[1] "B" "B" "A" "A"	[1] "A" "A" "B" "B"
[2] "B" "A" "B" "A"	[2] "A" "B" "B" "A"
[3] "B" "A" "A" "B"	[3] "A" "B" "B" "A"
[4] "A" "B" "A" "B"	[4] "B" "B" "A" "A"
[5] "B" "A" "A" "B"	[5] "B" "A" "B" "A"
[6] "A" "A" "B" "B"	[6] "A" "A" "B" "B"
[7] "B" "A" "B" "A"	[7] "B" "A" "B" "A"
[8] "A" "B" "A" "B"	[8] "A" "A" "B" "B"
[9] "B" "B" "A" "A"	[9] "B" "A" "A" "B"
[10] "B" "B" "A" "A"	[10] "B" "A" "B" "A"
[11] "B" "A" "A" "B"	[11] "B" "A" "A" "B"
[12] "B" "B" "A" "A"	[12] "A" "A" "B" "B"

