9.1 Statistical Hypotheses

STUDY AIMS:

- **AIM 1:** Determine whether virtual reality (vs. control) improves quality of life for residents and their adult children who live at a distance.
- **AIM 2:** Determine whether the positive effects of virtual reality (vs. control) on quality of life depend upon residents' level of cognitive impairment (MCI vs. mild to moderate AD/ADRD).
- **AIM 3:** Determine whether virtual reality (vs. control) reduces caregiver guilt for adult children and whether these effects depend on the adult child's own responses to the technology and their parent's responses to the technology.

- Primary Efficacy Endpoint(s):
 - Older adults
 - Quality of Life
 - Thriving
 - Positive and negative affectivity
 - Depression
 - Mental health symptoms
 - Loneliness and social connection
 - Relationship quality with adult child
 - Adult Children
 - Thriving
 - Positive and negative affectivity
 - Depression
 - Mental health symptoms
 - Caregiver guilt and perceived stress
 - Relationship quality with parent
- Secondary Efficacy Endpoint(s):
 - Older adults and adult children
 - Conversational, social, and emotional engagement during technology sessions
 - Kinesic (physical) engagement during technology sessions (older adult only)
 - Relationship connection and bonding during technology sessions

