The planned sample size needed to detect an effect size corresponds to the smallest of these effect sizes as our minimal detectable effect of interest – a conservative strategy that would give us adequate power. Various simulation studies were run, varying sample size, effect size of concurrent differences and longitudinal differences, and other model characteristics related to power (e.g., error variance and variance of the random effects). While the models for each aim vary in their specific effects, there are similarities across them. The moderating effects of cognitive impairment are the most specific effects, which would lend itself to lower power. Thus, these models were used as a lower bound for power in this grant and guided the decision on sample size, because if these ML-SEM models with moderation had sufficient power, we can be confident that our other proposed analyses would be sufficiently powered.

We specified a ML-SEM model that included a random effects regression model. We modeled the moderation by including an interaction term (4 conditions: treatment group x cognitive impairment) on its prediction of the fixed effect of quality of life for the Resident in T2-T5 and T6-T7. Additionally, we estimated concurrent differences across the four conditions, conservatively estimating that the effect was small across time ($d = .2$). Using parameter constraints, power was studied for concurrent differences between VR and control (e.g., at a given time point) as well as sustained gains over time between VR and Control.

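### H2b tests moderation of the VR effect on caregiver guilt by engagement measured only after allocation; this is not a randomised comparison, and the plan does not label it as associational

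*Combined protocol and SAP*

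**What the plan says.** **The hypothesis.** Section 2.1 (Aim 3, H2b) predicts that the "beneficial effects of the VR condition will be amplified when positive engagement is higher (vs. lower) for self and parent (a dyadic effect"). Section 9.1 repeats the question within Aim 3, asking "whether these effects depend on the adult child's own responses to the technology and their parent's responses to the technology", and lists caregiver guilt among the adult children's primary endpoints.

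**The moderator.** In the Section 1.3 schedule, the row "Technology sessions - Positive Engagement (self-report") is marked at T2 to T5 only, as is the behavioural-coding row. Section 4.1 makes engagement a secondary outcome, "measured through surveys, interviews, and observational methods during the intervention phase of the study". Section 2.1 expects the arms to differ on it: "Rendever should produce greater engagement than video chat because of the shared immersion into an altered reality". H1b and RQ2 use it as a mediator, and so does the objectives table in Section 3, which asks "whether these immediate responses mediate any impacts of the intervention on parent and adult child outcomes".

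**The analysis.** Section 9.4.2 assigns mixed models by name to Aims 1 and 2 and mentions multilevel structural equation models for dyadic tests in general. It gives H2b no covariates. The caution in Section 9.4.1 concerns additional exploratory work, including searches for moderators. The caution in Section 9.4.4 concerns analyses that are not pre-specified.

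**Cognitive level, for contrast.** It is fixed before allocation: Section 6.3 gives "Strata = 4 (UCSB/Rendever x MCI/Dementia"). The power model in Section 9.2 tests moderation by "including an interaction term (4 conditions: treatment group x cognitive impairment) on its prediction of the fixed effect of quality of life". Section 3 lists caregiver guilt under the objective on whether the technology effect depends on cognitive level.

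**The concern.** A moderator supports a randomised effect-modification claim when it is fixed before allocation, because the arms are then comparable within each of its levels. Engagement is itself a response to the assigned technology. Dyads who engage highly under VR and dyads who engage highly under Zoom are selected after allocation and may differ at baseline.

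A non-zero arm × engagement term can then arise in two ways other than engagement changing the VR effect:

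- **(a)** A baseline factor that predicts guilt is linked to engagement differently in the two arms. The term is then biased, in either direction.
- **(b)** The VR effect varies with a baseline factor that is linked to engagement. The term is then a real association, but not evidence that engagement causes the amplification.

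At stake is the reading of a named directional hypothesis on a primary outcome. A significant term would naturally be reported as engagement amplifying the benefit of VR, which the design cannot establish.

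**Working it through.** The plan gives no figure for H2b. The 0.85 power in Section 9.2 comes from arm × cognitive level on quality of life and does not bear on this point. What follows shows how the contrast behaves. **All links and effects are assumptions.**

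**Step 1: one moderator, by hand.** Take 96 dyads per arm (Section 9.2) and a baseline trait U. Engagement has unit variance in each arm and correlates with U by l_VR or l_Zoom. Guilt has unit variance and correlates with U by −g. Neither VR nor engagement affects guilt.

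- Slope of guilt on engagement within an arm: −g·l
- Interaction: −g(l_VR − l_Zoom)
- Residual variance in an arm: 1 − (g·l)²
- Standard error: √[(residual variance VR + residual variance Zoom)/96]
- Rejection (two-sided 5%): P(Z > 1.96 − z) + P(Z < −1.96 − z), where z = |interaction|/SE

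| l_VR / l_Zoom | g | Interaction | SE | Rejection |
|---|---|---|---|---|
| 0.5 / 0.5 | 0.3 | 0 | 0.143 | 5% |
| 0.6 / 0.3 | 0.3 | −0.09 | 0.143 | 9.7% |
| 0.6 / 0.3 | 0.5 | −0.15 | 0.140 | 18.8% |
| 0.7 / 0.2 | 0.3 | −0.15 | 0.143 | 18.3% |
| 0.7 / 0.2 | 0.5 | −0.25 | 0.140 | 43.4% |

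Simulation (4,000 trials each) gave 5%, 9-10%, 18%, 18% and 41-43%. Reversing the links to 0.3/0.6 gave 9-19% with the opposite sign.

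For case (b), let the VR effect on guilt be −h·U with equal links l. The slopes are −(g + h)l in VR and −g·l in Zoom, so the interaction is −h·l. With h = 0.3 and l = 0.5 this is −0.15.

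**Step 2: own and parent engagement together.** This is a joint 2-df test at 5%, with 5,000 trials per setting.

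- n = 192 × 0.85 = 163 dyads (Section 9.2).
- Closeness C1 is linked to both engagements, and cognition C2 to the parent's.
- Engagement is 0.8 SD higher in VR.
- T1 guilt = −0.3·C1 + residual.
- Mean T6-T8 guilt = −(0.3 + c1)C1 − c2·C2 − arm × (h1·C1 + h2·C2) + residual.
- The average VR effect is 0, the person-level share 0.6 and covariate reliability 0.8.

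Unless a row says otherwise, links are C1 0.5 and C2 0.3. Rejection rates, in %:

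| Setting | Change score | T1 guilt as covariate | + baseline main effects | + arm × bonding, arm × stratum |
|---|---|---|---|---|
| Equal links, constant VR effect (c1 0.3, c2 0.2) | 5.0 | 5.0 | 4.8 | 5.0 |
| (a) mild: Zoom/VR links C1 0.3/0.6, C2 0.2/0.4 (c1 0.2, c2 0.2) | 9.1 | 13.9 | 4.9 | 5.1 |
| (a) strong: C1 0.2/0.7, C2 0.1/0.4 (c1 0.3, c2 0.2) | 24.2 | 39.6 | 6.1 | 9.5 |
| (b) closeness, h1 = 0.2 | 16.0 | 19.4 | 19.3 | 5.2 |
| (b) closeness, h1 = 0.3 | 29.8 | 37.8 | 39.5 | 5.2 |
| (b) cognition, h2 = 0.2 | 7.2 | 8.0 | 8.3 | 5.4 |
| (b) cognition, h2 = 0.3, C2 link 0.5 | 20.8 | 27.5 | 27.8 | 9.0 |

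In the (b) rows c1 = c2 = 0. Those rejections pick up a real association and are errors only under a causal reading.

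Baseline main effects remove most of case (a) but none of case (b). The arm × covariate terms remove most of case (b), yet in strong case (a) they raise rejection from 6.1% to 9.5%. Other codings of that last cell gave 8% to 18%, depending on how family bonding is represented.

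Section 1.2 implies 372/2 = 186 dyads, 166 after 20 dyad losses, and 154 if all 12 individual losses were adult children. At n = 154 the h1 = 0.3 row is 27.1 / 33.9 / 35.8 / 5.6%.

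**Step 3: cost of the extra terms.** The standard errors of the own and parent interactions rise from 0.101 to 0.113 (×1.12) and from 0.102 to 0.117 (×1.15).

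**Step 4: the randomised alternative.** The standard error for arm × cognitive stratum is 0.19-0.23 SD. A 0.2 SD difference between strata gives z = 0.87 to 1.05 and power of about 14-18%. A 0.4 SD difference gives z = 1.74 to 2.11 and about 41-56%.

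**The case against.** - **H2b can be read descriptively.** It says the benefit is larger when engagement is higher, not because of it. Under that reading case (b) is a true finding. This stands, and case (b) is therefore treated here as a limit on interpretation, not as bias. Case (a) remains bias under either reading.
- **No H2b regression is written down, and no baseline covariates are named for any hypothesis.** This also stands; the tests above are constructions. But any model of H2b as stated must compare the engagement slope between arms, and that contrast is the problem.
- **The inputs are assumed.** This stands. Phase I had no control group (Section 9.2), so no document compares engagement links between VR and Zoom. Its cognition signals were mixed: higher MMSE-2 went with more engagement in one VR session, immersion went the other way, and enjoyment did not differ.
- **A randomised moderation question on guilt is already in the plan.** This stands. Section 3 lists it, so it needs only to be pointed to.

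A reader might go further and infer that the H2b test will give a false positive, or that Aim 3 as a whole is unsound. The documents support neither. The neutral setting rejects at 5%, nothing shows that links differ by arm, and H2a compares the arms as randomised.

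**Conclusion.** The point holds as a limit on what H2b can show. That arm × engagement is not a randomised comparison follows from the measurement schedule alone and needs no simulation.

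The size of any distortion is unknown. Over the assumed range of arm-specific links, rejection with no modification by engagement runs from 5% (equal links) to about 43%, in either direction. If the VR effect varies with a baseline factor, the term reflects a real association with no claim on engagement as the cause. Neither existing caution covers a stated hypothesis.

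The consequence is confined to H2b and its interpretation. H2a and RQ1 stand. It should be changed, because the label and the covariates cost little.

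**What to change.** 1. State that H2b will be reported as a non-randomised association, with no causal effect-modification claim.
2. In the H2b model, adjust for baseline variables already collected: T1 caregiver guilt, T1 family bonding of both members, cognitive stratum and site. Do not describe T1 measures as pre-allocation unless T1 is shown to precede disclosure of the arm; Section 1.3 lists randomisation at the consent visit.
3. As a sensitivity analysis, add arm × family bonding and arm × cognitive level. Say that these terms raise the standard errors by about 12-15%, address only effect variation with a baseline factor, and can slightly raise the error when links differ by arm.
4. For the randomised effect-modification question, refer to the arm × cognitive-level analysis of caregiver guilt already among the Section 3 objectives. Report it as an estimate with its interval, since its power is low.

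**Cost.** This needs SAP wording only, with no new data. H2b becomes a weaker claim, and residual confounding remains through unmeasured factors and error in the covariates. Section 1.2 already reports attrition over the whole trial; if analysis has begun, label these changes post hoc.

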2.2 Background

Cognitive decline in older adults is a public health crisis, with high costs to society and few preventative measures or solutions. Alzheimer's disease affects approximately 5.4 million Americans and it is estimated that by 2050, this number will more than double to 13.8 million. The cost of caring for adults with Alzheimer's disease (AD) and Alzheimer's disease-related dementias (ADRD) in health care, long-term care, and hospice in 2019 was \$244 billion. What is equally pressing, however, are the emotional and relational costs of dementia for older adults and the family members who love and care for them. New technologies are essential that can reduce the caregiver burden of AD/ADRD (NIA's strategic plan). Before COVID-19, family members were already concerned about the quality of care provided for their loved one with dementia in senior living communities and these concerns have been amplified by the pandemic. The virtual reality (VR) program, Rendever, provides an innovative and affordable solution to these challenges by enabling older adults in senior living communities to maintain important family relationships, engage fully with life, and reconnect with their past, regardless of physical location, through its advanced networking and live streaming capabilities. There is neurological, behavioral, and physiological evidence that virtual environments allow people to feel the emotional presence of others in ways that surpass their location in space. Unfortunately, little research has examined VR's impact on older adults' social relationships, primarily due to the lack of networking and communication capabilities of other VR programs.

In our Phase I study, we tested the feasibility of Rendever with residents with mild cognitive impairments (MCI) or mild to moderate dementia and their family members who lived at a distance. Our metrics for both Aims were exceeded. Data collected with 21 family dyads showed Rendever to be safe, easy to use, and transformative for the families. Residents and their family members reported extremely high user satisfaction, enjoyment, and immersion. Rendever also significantly reduced residents' feelings of isolation, increased positive affect, decreased negative affect, increased quality of life, and improved emotional closeness with family members over time compared to baseline. In addition, it significantly improved mental health and reduced negative affect and caregiver guilt for the family member over time compared to baseline. Residents with MCI and mild to moderate dementia also equally enjoyed the VR. In Phase II (the current project described), we continue to refine the long-distance features of Rendever, while expanding the scientific goals of the project by testing the immediate and longer-term impact of Rendever on the quality of life of residents and their adult children in an experimental design. We also continue to investigate whether residents' responses to the VR depend upon their level of cognitive impairment. Resident-adult child dyads (N=200) will participate. Half of the residents will have MCI and half will have mild to moderate dementia. The dyads will be randomly assigned to a VR group or an active control group of video chat (Zoom).

